## Pseudocode for Superlearner and Candidate Estimators

Let  $A_z$  denote observed data from participants in treatment stratum  $z$  in a single AMP trial.

---

### Algorithm 1 Superlearner and candidate estimators

---

**Input:**  $A_z$  and  $\widehat{\psi}_1, \dots, \widehat{\psi}_K$  prediction algorithms

- 1: Use  $A_z$  to impute  $A_z^*$  via package `missForest`
  - 2: Use package `survtmle` on  $A_z^*$  to obtain  $\widehat{D}_i^{(1)}$  and  $\widehat{D}_i^{(2)}, \forall i \in A_z^*$  †
  - 3: Partition  $A_z^*$  into 10 folds, with  $A_{z,1}^*, \dots, A_{z,10}^*$  denoting validation sets
  - 4: **for**  $j = 1, \dots, 10$  **do**
  - 5:   **for**  $k = 1, \dots, K$  **do**
  - 6:     Fit  $\widehat{\psi}_{k,j}$  on training set  $A_{z,-j}^*$  pertaining to  $A_{z,j}^*$  ‡
  - 7:     Let  $j(i) = j$  for all  $i \in A_{z,j}^*$
  - 8:   **end for**
  - 9: **end for**
  - 10: Using  $\{\widehat{\psi}_{k,j(i)}(W_i), \widehat{D}_i^{(1)}, \widehat{D}_i^{(2)} : i \in A_z^*, k \in \{1, \dots, K\}\}$ , obtain optimal  $\boldsymbol{\alpha} = (\alpha_1, \dots, \alpha_K)$  using package `nloptr`
  - 11: Repeat steps 3–10 five times to obtain  $\boldsymbol{\alpha}^* = \frac{1}{5} \sum_{r=1}^5 \boldsymbol{\alpha}^{(r)}$
  - 12: **for**  $k = 1, \dots, K$  **do**
  - 13:   Fit algorithm  $\widehat{\psi}_k$  on  $A_z^*$  ‡
  - 14: **end for**
  - 15: Let  $\widehat{\psi}_{SL}(w) = \sum_{k=1}^K \alpha_k^* \widehat{\psi}_k(w)$
- Output:**  $\widehat{\psi}_k(W_i), k = 1, \dots, K$ , and  $\widehat{\psi}_{SL}(W_i)$  for all  $i \in A_z^*$
- 

† Following Section 3 in the KwaZulu-Natal risk prediction SAP, `survtmle` is run twice to obtain the individual  $i$ -specific quantities  $\widehat{D}_i^{(1)}$  and  $\widehat{D}_i^{(2)}$ , defined as the sum of the point estimate of the marginal survival probability  $P(T \in (t_0, t_1])$  and  $P(T > t_1)$ , respectively, plus the corresponding individual  $i$ -specific efficient influence function estimate output by `survtmle`.  $\widehat{D}_i^{(1)}$  and  $\widehat{D}_i^{(2)}$  are then used to estimate the cross-validated risk, which is minimized with respect to the superlearner weights.

‡ Some data adaptive algorithms such as `glmnet` may require another layer of cross-validation.

## Pseudocode for Internal Validation Algorithm

Let  $A_z$  denote observed data from participants in treatment stratum  $z$  in a single AMP trial.

---

### Algorithm 2 Internal Cross-validation

---

**Input:**  $A_z$  and  $\widehat{\psi}_1, \dots, \widehat{\psi}_K$  prediction algorithms

- 1: Partition  $A_z^*$  into 10 folds, with  $A_{z,1}^*, \dots, A_{z,10}^*$  denoting validation sets
  - 2: **for**  $s = 1, \dots, 10$  **do**
  - 3:   Use training set  $A_{z,-s}$  to impute  $A_{z,-s}^*$  via package `missForest`
  - 4:   Use package `survtmle` on  $A_{z,-s}^*$  to obtain  $\widehat{D}_{s,i}^{(1)}$  and  $\widehat{D}_{s,i}^{(2)}, \forall i \in A_{z,-s}^*$  †
  - 5:   Partition  $A_{z,-s}^*$  into 10 folds, with  $A_{z,-s,1}^*, \dots, A_{z,-s,10}^*$  denoting validation sets
  - 6:   **for**  $j = 1, \dots, 10$  **do**
  - 7:     **for**  $k = 1, \dots, K$  **do**
  - 8:       Fit  $\widehat{\psi}_{k,j}$  on training set  $A_{z,-s,-j}^*$  pertaining to  $A_{z,-s,j}^*$  ‡
  - 9:       Let  $j(i) = j$  for all  $i \in A_{z,-s,j}^*$
  - 10:     **end for**
  - 11:   **end for**
  - 12:   Using  $\{\widehat{\psi}_{k,j(i)}(W_i), \widehat{D}_{s,i}^{(1)}, \widehat{D}_{s,i}^{(2)} : i \in A_{z,-s}^*, k \in \{1, \dots, K\}\}$ , obtain optimal  $\alpha = (\alpha_1, \dots, \alpha_K)$  using package `nloptr`
  - 13:   Repeat steps 5–12 five times to obtain  $\alpha_s^* = \frac{1}{5} \sum_{r=1}^5 \alpha^{(r)}$
  - 14:   **for**  $k = 1, \dots, K$  **do**
  - 15:     Fit algorithm  $\widehat{\psi}_k$  on  $A_{z,-s}^*$  ‡
  - 16:   **end for**
  - 17:   Let  $\widehat{\psi}_{SL,s}(w) = \sum_{k=1}^K \alpha_{s,k}^* \widehat{\psi}_k(w)$
  - 18:   Let  $s(i) = s$  for all  $i \in A_{z,s}$
  - 19: **end for**
  - 20: Use  $A_z$  to impute  $A_z^*$  via package `missForest`
  - 21: Use package `survtmle` on  $A_z^*$  to obtain  $\widehat{D}_i^{(1)}$  and  $\widehat{D}_i^{(2)}, \forall i \in A_z^*$  †
  - 22: Compute  $\widehat{AUC}_{CV}$  for each  $\widehat{\psi}_k$  and  $\widehat{\psi}_{SL}$  using  $\{\widehat{\psi}_{k,s(i)}(W_i), \widehat{\psi}_{SL,s(i)}(W_i), \widehat{D}_i^{(1)}, \widehat{D}_i^{(2)} : i \in A_z^*\}$
- Output:**  $\widehat{AUC}_{CV}$  for  $\widehat{\psi}_k, k = 1, \dots, K$ , and  $\widehat{\psi}_{SL}$  for  $A_z^*$
- 

† Following Section 3 in the KwaZulu-Natal risk prediction SAP, `survtmle` is run twice to obtain the individual  $i$ -specific quantities  $\widehat{D}_i^{(1)}$  and  $\widehat{D}_i^{(2)}$ , defined as the sum of the point estimate of the marginal survival probability  $P(T \in (t_0, t_1])$  and  $P(T > t_1)$ , respectively, plus the corresponding individual  $i$ -specific efficient influence function estimate output by `survtmle`.  $\widehat{D}_i^{(1)}$  and  $\widehat{D}_i^{(2)}$  are then used to estimate the cross-validated risk, which is minimized with respect to the superlearner weights.

‡ Some data adaptive algorithms such as `glmnet` may require another layer of cross-validation.

## 9 Trial Monitoring

The AMP trials are monitored in four ways: (1) feasibility monitoring for retention and adherence to infusions; (2) sequential monitoring of prevention efficacy; (3) monitoring for futility to assess prevention efficacy, defined as an inability to answer the primary efficacy objective in a timely manner; and (4) operational monitoring for other performance standards of quality of trial conduct. Data on these monitoring activities are collated into interim reports and are presented to the independent DSMB every 6 months. While guidelines for trial modifications based on the monitoring operate separately for the two AMP trials, the same multinational DSMB monitors the two trials, facilitating its ability to account for all information when making recommendations. Following each DSMB meeting, the DSMB reports to the Oversight Committee (OC) a summary of the trial review, which may include recommendations to modify or terminate the trial for one or both study cohorts. The following descriptions apply to each trial separately.

### 9.1 Feasibility Check and Guideline for Continuing Enrollment as Planned

A feasibility monitoring report is developed as soon as approximately and not fewer than 120 enrolled participants have expected follow-up through to the end of the Week 32 visit window. This feasibility monitoring is based on the first four 8-week infusion intervals (Weeks 1 through 32) and evaluates whether an adequately high percentage of participants attend clinical visits and receive the infusions per the protocol.

The guideline is based on an adequately high rate of study participation (participants remain engaged in the trial and have not declined further infusions) supplemented by data on visit attendance, which corresponds to adherence to receipt of infusions.

As stated in the protocol, the following guideline is used for continuing enrollment as planned:

- Continued participation by the Week 32 visit pooled over the three treatment groups is greater than 80%.

If this treatment group-blinded criterion fails to be met, the Protocol Team, in discussions with the DSMB and OC, will discuss whether modification or termination of the trial is warranted.

Here we expand upon the details of the feasibility guideline and on the output included in the feasibility check monitoring report.

Discontinued participation is assessed using multiple event definitions indicating discontinued participation, in order to capture different reasons for discontinuation that have different

impacts on the ability of the trials to meet their primary efficacy objectives. In particular, the following five definitions (with their purposes summarized) will be analyzed:

1. CRF-confirmed permanent discontinuation of study product administration prior to study completion, with discontinuation due to a safety issue or refusal to continue taking infusions. [*Addresses if infusions are too onerous*]
2. The same as Definition 1 except only including discontinuation due to a safety issue [*Addresses if infusions are too onerous due to a safety issue*]
3. The same as Definition 1 except only including discontinuation due to refusal to continue undergoing infusions. [*Addresses if infusions are considered too onerous due to a non-safety reason*]
4. Permanent discontinuation of study product administration for any reason other than a safety issue or refusal to continue taking infusions. This definition includes CRF-confirmed study termination due to lost contact with participant or 20 consecutive weeks without any participant contact. [*Addresses discontinued infusions or loss to follow-up for reasons other than safety or refusal, with no information available on whether the loss was related to infusions being onerous*]
5. The first event of Definitions 1 and 4 [*Addresses discontinued infusions for any reason including loss to follow-up*]

Definition 1 aims to measure discontinued participation due to the infusion process being too onerous, which could occur either because of a safety issue or because of refusal to continue receive infusions. Definitions 2 and 3 measure discontinued participation due to the two component events comprising Definition 1 (safety and refusal, respectively), thereby isolating two reasons for discontinued infusions. These types of discontinued participation are the most serious in that a high rate would indicate an infeasibility of the VRC01 intervention, and therefore Definitions 1, 2, 3 are the most important for measuring feasibility of the intervention. As such the 80% feasibility guideline is interpreted primarily for Definition 1.

Definition 4 measures discontinued participation due to reasons other than safety or refusal including loss to follow-up, which is based on either CRF-confirmed loss or an operational definition of a loss to follow-up event not captured on a CRF. Given that loss to follow-up is expected to frequently occur for reasons different from the infusion process being too onerous (i.e., for reasons that would occur in efficacy trials of other HIV prevention interventions, such as moving), this type of discontinued participation is less serious, where the study could still be made feasible under moderate rates of loss to follow-up, by enrolling additional study participants.

Definition 5 counts as discontinued participation any reason for discontinuation or loss to follow-up, whichever occurs first. Thus this definition measures permanent ceasing of infusions without distinguishing the reason.

For each definition of discontinued participation, the analysis counts discontinued participation events. First, we define discontinued participation as a record on a CRF confirming permanent discontinuation of study product administration prior to study completion, with discontinued participation by Week 32 defined as this date occurring before or on the Week 32 visit date, or, if the visit was not yet attended, before or on the date defining the end of the Week 32 visit window. For Definition 5, the Kaplan-Meier estimator will be used to estimate and display the probability of discontinued participation over time, starting at study entry through to the time period during which data are available (which will extend at least through the Week 32 visit window). For all other definitions, a competing risks failure time analysis is used that studies the time until the first event of a type specified in a given definition. For these competing risks analyses a participants follow-up is right-censored by the occurrence of another discontinuation event type that is not included in the definition under consideration. For these competing risks analyses each time-to-event curve is estimated using the Aalen-Johansen estimator, which in particular yields an estimate of the probability of discontinuation due to the event type by the Week 32 visit. For Definition 1 right-censoring is by loss to follow-up (using the operational Definition 4); for Definition 2 right-censoring is by loss to follow-up (using the operational Definition 4) and by discontinuation due to refusal; for Definition 3 right-censoring is by loss to follow-up (using the operational Definition 4) and by discontinuation due to a safety issue; and for Definition 4 right-censoring is by discontinuation due to Definition 1 (a safety issue or refusal).

Appendix A includes mock tables on expected versus observed visit attendance (Table 5A) and on infusion adherence (Table 5B) patterns that will be reported at the 6-monthly DSMB meetings. All of this output will be included in the feasibility check monitoring report, focusing on the first five infusion visits (Week 0, 8, 16, 24, 32).

## 9.2 Sequential Monitoring of Prevention Efficacy for Potential Harm, Non-Efficacy, and High Efficacy

For each trial, PE is monitored by the independent DSMB at each DSMB meeting, with triggers based on numbers of primary HIV-1 infection endpoints for when the DSMB meetings begin to include formal evaluation of the potential harm, non-efficacy, and high efficacy stopping boundaries (these triggers are described below). The approach to sequential monitoring of PE is similar to that described in Gilbert, Grove et al. (2011). The monitoring of PE in the AMP trials is also similar to that used for the HVTN 505 phase 2b HIV-1 vaccine efficacy trial (Hammer et al., 2013). Each of the AMP trials uses sequential monitoring of the pooled mAb groups versus control to stop early for:

- potential harm [establish that PE (pooled over the mAb groups)  $< 0\%$  based on a 2-sided monitoring-adjusted 90% confidence interval lying below 0%]
- non-efficacy [establish that PE (pooled over the mAb groups)  $< 40\%$  based on a 2-sided 95% nominal confidence interval lying below 40%]

Table 3: Summary of sequential monitoring of PE for each AMP trial

Monitoring Type	Hypotheses	Testing Approach	Size/Power	Monitoring Plan	Number of Interim Analyses
Potential Harm	$H_0 : PE \geq 0\%$ vs. $H_1 : PE < 0\%$	Exact 1-sided binomial test of the proportion of infections assigned to a mAb group	1-sided $\alpha = 0.05$	Near-constant* 1-sided p-value cut-off controlling the FWER at $\alpha = 0.05$	After every infection from 20 th total until first non-efficacy analysis
Non-Efficacy	$H_0 : PE \geq 40\%$ vs. $H_1 : PE < 40\%$	Wald test	1-sided $\alpha = 0.025$	Nominal 2-sided 95% CI supplemented with conditional power	6-monthly starting after at least 45 but no more than 67 total infections †
High Efficacy	$H_0 : PE \leq 70\%$ vs. $H_1 : PE > 70\%$	Wald test	1-sided $\alpha = 0.025$	Nominal 2-sided 95% CI	6-monthly starting at the same time as for non-efficacy

\*An increasing per-test alpha until a constant level is reached that, if applied to all subsequent tests, maintains the specified FWER

†The first non-efficacy/high efficacy interim analysis occurs either at the scheduled DSMB meeting at which there are 45 or more primary endpoint events across the three study groups or when 67 total primary endpoint events are observed, whichever occurs earlier.

- high efficacy [establish that PE (pooled over the mAb groups)  $> 70\%$  based on a 2-sided 95% nominal confidence interval lying above 70%].

The sequential monitoring for non-efficacy and high-efficacy is based on 2-sided 95% confidence intervals in order that the result of the study that would be reported in the abstract of a journal article would convey convincing evidence supporting the conclusion of non-efficacy or high efficacy. Freidlin, Korn, and Gray (2010) discuss a rationale for this approach to non-efficacy monitoring. The sequential monitoring for potential harm is based on 2-sided 90% confidence intervals for prudence to protect the safety of study participants, i.e., less precision is required to meet a guideline for potential harm than to meet guidelines about non-efficacy or high efficacy. The sequential monitoring plan for each AMP trial is summarized in Table 3.

The potential harm monitoring is done after every primary endpoint event starting at the 20th total pooled over the three treatment groups, through to the time at which the non-efficacy/high efficacy monitoring commences. Once the non-efficacy/high efficacy monitoring begins, the non-efficacy monitoring serves the purpose of detecting a harmful effect of the mAb to elevate the endpoint rate compared to control. The details of the procedures used for the three monitoring guidelines are described next. In addition to these monitoring guidelines that are based on parameters aggregating all primary HIV-1 infection events over follow-up,

the statistical reports including non-efficacy/high efficacy monitoring will also graphically report estimates of cumulative HIV-1 incidence over time by study arm and estimates of cumulative prevention efficacy over time for high dose vs. placebo and for low dose vs. placebo.

### 9.2.1 Potential harm monitoring

Heyse et al. (2008) and the HVTN 505 phase 2b HIV-1 vaccine efficacy trial (Hammer et al., 2013) are examples of randomized, placebo-controlled efficacy trials that used continuous monitoring for an elevation in the endpoint rate in the active versus control treatment arm. Continuous monitoring means that an unblinded statistician has visibility to the treatment assignment of each diagnosed MITT HIV-1 infection as they are determined in real-time, and, after each confirmed HIV-1 infection diagnosis, this statistician notes whether a stopping boundary is reached that indicates that the relative cumulative rate of HIV-1 infection (RR, pooled mAb group/control) exceeds one. If the stopping boundary is met, then the unblinded statistician immediately informs the Chair of the DSMB and the Executive Secretary of the DSMB through secure communication procedures. As such, the potential harm monitoring is in real-time, with a result possible at any time, whereas in contrast the non-efficacy and high efficacy monitoring is conducted only at the 6-monthly scheduled DSMB meetings or at any extra DSMB meetings requested by the DSMB (with exception that the first non-efficacy analysis would be done and reported to the DSMB by secure means prior to a scheduled DSMB meeting if the 67th total primary endpoint event occurs prior to a non-efficacy analysis triggered by at least 45 endpoints by a scheduled DSMB meeting, as described in Table 3).

The potential harm monitoring is done using an exact one-sided binomial test of the null hypothesis  $H_0 : p \leq 2/3$  versus the alternative hypothesis  $H_1 : p > 2/3$ , where  $p$  is the probability that an HIV-1-infected participant was assigned to either of the two mAb groups (as compared to being assigned to the control group). The tests start at the 20th total infection through to the infection count at which the non-efficacy/high efficacy monitoring commences, which is a minimum of 45 and is a random variable that depends on the timing of DSMB meetings (this value is referred to as the  $n^{\text{th}}$  infection). Based on protocol projections we assume that  $n^*$  is at most 67, which is useful for setting the critical values of the test. (If the highly unlikely result occurs that  $n^*$  exceeds 67, then the first non-efficacy analysis would be conducted based on 67 infections, which would serve the purpose of potential harm monitoring. The number 67 is chosen because that is the infection count at which a point estimate of zero PE would just correspond to an upper nominal 95% confidence bound for PE equal to 0.40; this approach to starting non-efficacy monitoring was suggested by Freidlin, Korn, and Gray (2010).) Each test is performed at a prespecified nominal/unadjusted alpha-level, which may vary over the multiple tests. The alpha-level used for each test is determined indirectly as follows: we must first choose the overall type I error rate we are willing to accept over the course of the monitoring (the overall probability that we reach a stopping boundary during the trial, when the mAb is actually safe, i.e., true  $RR = 1$ , equivalently  $p = 2/3$ ); and secondly we must choose whether/how to vary the alpha-level from test-to-test. Using

Table 4: Potential harm monitoring stopping boundaries for each AMP trial: One-sided p-value cut-offs for rejecting  $H_0 : p \leq 2/3$  in favor of  $H_1 : p > 2/3$  with an exact 1-sided binomial test where  $p$  is the probability that an HIV-1-infected participant was assigned to one of the two mAb groups

No. of Infections in VRC01 Groups	No. of Infections in Control Groups	Per-Test Type I Error Rate (1-Sided P-value Cut-off)
20	0	0.003
20	1	0.013
20	2	0.018
22	3	0.018
25	4	0.018
28	5	0.018
31	6	0.018
34	7	0.018
37	8	0.018
40	9	0.018
43	10	0.018
45	11	0.018
48	12	0.018
54	13	0.018

these pieces of information we determine the exact alpha-levels to be used for each test.

An overall 1-sided type I error rate of 0.05 is chosen for the family-wise error rate of the multiple hypothesis tests starting at the 20th HIV-1 infection endpoint through to the 67th. This type I error rate is chosen to balance the competing goals of participant safety and preventing false positive results. To prevent stopping too early, perhaps due to spurious results caused by wide sampling variability, stopping prior to the accumulation of 20 total infections was ruled out (the 2:1 mAb:control allocation ratio leads to this choice; in contrast a 1:1 allocation ratio would lead to starting at about 12 total infections). Table 4 shows the potential harm stopping boundaries in terms of the one-sided p-value cut-offs for a selected set of potential harm interim analyses starting at the 20th HIV-1 infection event.

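### SAP Table 4 is ambiguous as a real-time harm boundary: at the 21st infection its printed cut-off and counts disagree on 19/2, and row 54/13 is not the first crossing for 13 control infections

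*SAP*

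**What the plan says.** SAP 9.2.1 monitors for harm in real time: "after each confirmed HIV-1 infection diagnosis, this statistician notes whether a stopping boundary is reached", and if one is reached the DSMB Chair and Executive Secretary are told at once. The test is an "exact one-sided binomial test of the null hypothesis" that p is at most 2/3, where p is the "probability that an HIV-1-infected participant was assigned to either of the two mAb groups". Looks begin at the 20th infection ("stopping prior to the accumulation of 20 total infections was ruled out") and end when non-efficacy monitoring starts, at 67 infections at the latest. SAP 9.2.1 also states: "An overall 1-sided type I error rate of 0.05 is chosen for the family-wise error rate of the multiple hypothesis tests", from the 20th infection to the 67th.

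Table 4, whose caption begins "Potential harm monitoring stopping boundaries for each AMP trial: One-sided p-value cut-offs for rejecting", has 14 rows, written here as VRC01/control. The cut-off is 0.003 for 20/0, 0.013 for 20/1 and 0.018 for the other twelve: 20/2, 22/3, 25/4, 28/5, 31/6, 34/7, 37/8, 40/9, 43/10, 45/11, 48/12 and 54/13. The text calls these a selection of the interim analyses. SAP Table 3 describes a per-test level that rises to a constant. The footnote to protocol Table 4-6 places the thresholds after each infection in a separate monitoring plan.

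**The concern.** Table 4 gives two things that can be compared with the accruing data: counts and p-value cut-offs. A reader should reach the same decision from either. At the 21st infection the printed digits do not allow that for 19/2.

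The last row raises a different problem. In the ten rows from 22/3 to 48/12, the VRC01 count is the first that crosses 0.018 for that number of control infections, so those rows can be read as the threshold for each control count. Row 54/13 cannot be read that way, and nothing marks the change.

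At stake are the timing of a safety alert in each AMP trial and whether the stated 0.05 family-wise error describes the rule actually applied.

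**Working it through.** **Inputs.** Null probability 2/3, from the 2:1 allocation (SAP 9.2.1). Looks at totals n = 20 to 67. Cut-offs and counts from Table 4.

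**Formula.** For v VRC01 and c control infections, n = v + c and the p-value is the sum over k = v to n of C(n,k)(2/3)^k(1/3)^(n−k).

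**Reproducing the table.** At each row's own total I found the smallest VRC01 count with p at or below the printed cut-off. Thirteen of the 14 rows match exactly. Examples:
- n = 20: 20/0 has p = 0.0003; 19/1 has 0.0033, above 0.003.
- n = 56: 45/11 has p = 0.0179, just under 0.018.
- n = 67: 54/13 has p = 0.0088; 53/14 has 0.0183, above 0.018.

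The exception is n = 21.

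**The 21st infection.**
- 19/2: 2^19(210 + 42 + 4)/3^21 = 2^27/3^21 = 134,217,728/10,460,353,203 = 0.01283, below 0.013.
- 20/1: 2^20(21 + 2)/3^21 = 0.0023.

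On the printed digits the minimum at n = 21 is therefore 19, not the listed 20. Row 20/2 has the same difficulty. It can be reached only from 19/2 or 20/1; 20/1 is itself a listed stop, so 20/2 can be a first stop only if 19/2 does not stop. Any unrounded cut-off from 0.0125 up to just under 0.01283 prints as 0.013, excludes 19/2 and makes all 14 rows consistent.

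For hazard ratio h, an infection falls in a VRC01 arm with probability 2h/(2h + 1): 2/3, 0.75 and 0.80 for h = 1, 1.5 and 2. The chance of being at 19/2 after 21 infections is then 1.1%, 5.5% and 12.1%.

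**Thirteen control infections.**

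| VRC01/control | n | p |
|---|---|---|
| 50/13 | 63 | 0.0195 |
| 51/13 | 64 | 0.0161 |
| 52/13 | 65 | 0.0132 |
| 53/13 | 66 | 0.0108 |
| 54/13 | 67 | 0.0088 |

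The first crossing of 0.018 at 13 controls is 51. Row 54/13 can be reached only from 53/13, which has already crossed, or from 54/12, which is past the listed 48/12. Under 0.018 it can never be where monitoring first stops. In the ten rows from 22/3 to 48/12, one VRC01 infection fewer gives p between 0.0189 and 0.0220, so each of those is a first crossing.

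**Family-wise error and harm-stop probability.** I carried the probability of each (v, c) forward one infection at a time, removed any state that stops at n = 20 to 67, and summed what was removed.

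| Reading of Table 4 | HR 1 | HR 2 |
|---|---|---|
| Printed cut-offs taken literally (19/2 and 51/13 stop) | 0.0518 | 69.6% |
| 21st-infection cut-off between 0.0125 and 0.01283 (19/2 continues, 51/13 stops) | 0.0501 | 69.5% |
| Counts as minima per control count (19/2 continues, 54 needed at 13 controls) | 0.0488 | 68.2% |

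**The case against.** The strongest reply is that the rule is one test per total infection count and that Table 4 is openly a selection of those tests. On that reading 54/13 is the look at 67 infections, where 54 is exactly the smallest crossing count, and 51/13 belongs to the look at 64, which the table need not list. This stands. A reader might infer that 54/13 contradicts 0.018, or that the row is an error for 51/13; the documents support neither.

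For 19/2 the reply is rounding. SAP 9.2.1 says exact levels are determined for each test, so three-decimal values are naturally read as rounded, and a value such as 0.0127 removes the conflict. This is probably what happened, but the SAP does not print the value, so the table alone cannot settle it.

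A reader might also infer that the trial's error control fails. That goes too far. The 0.0518 needs the rounded digits to be treated as exact and harm looks to run to at least the 64th infection; the same cut-offs give 0.0401 through the 45th and 0.04995 through the 63rd. Harm looks may end anywhere from 45 to 67.

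Finally, the protocol places the full boundaries in the monitoring plan, which was not available. The statistician may work from that plan and compute the p-value directly, in which case neither ambiguity bites. That lowers the practical risk but does not repair a SAP table captioned as the stopping boundaries.

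**Conclusion.** The point holds as an ambiguity in presentation, in two places. At the 21st infection, the printed cut-off and the listed counts give different decisions for 19/2; rounding is the likely cause. At 13 controls there is no contradiction, only an unlabelled row that does not follow the first-crossing pattern of rows 22/3 to 48/12. Misreading it as a threshold would delay the alert by up to three VRC01 infections (51, 52 and 53).

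The numerical effect is small. Family-wise error is 0.0518 with the cut-offs as printed and 0.0501 with the rounding explanation. At a hazard ratio of 2, the harm-stop probability differs by 1.3 percentage points (69.5% against 68.2%) between 51 and 54 at 13 controls. These figures assume 2:1 risk under the null, independent infections, a look after every infection and harm monitoring through the 67th. It remains worth correcting because the boundary is checked after every infection and governs a safety alert.

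**What to change.** Recompute Table 4 from the unrounded cut-offs that meet the 0.05 family-wise error, and print them to at least four decimals. Give the minimum crossing VRC01 count for every total from 20 to 67. Alternatively, give the first crossing for each control count from 0 to 13, which under 0.018 is 51 at 13 controls. If 54/13 is kept, label it as the look at the 67th infection. State whether the counts or the cut-offs govern, so that the treatment of 19/2 is explicit. Check the result against the monitoring plan and reconcile any difference. The cost is one corrected table and a sentence in the SAP, with the same check in the monitoring plan; design, data collection and the primary analysis are unaffected.
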